1. INTRODUCTION

The purpose of this reporting and analysis plan (RAP) is to describe the analyses of Group 2 to be included in the Clinical Study Report for Protocol:

Revision Chronology:		
2016N281575_00	2016-AUG-22	Original
2016N281575_01	2016-OCT-10	Section 6.2: Inclusion of information on CE marking.
2016N281575_02	2018-JAN-04	Update to PK collection procedures and implementation of in-stream PK data analysis. Update to location of Secondary Medical Monitor contact information.
2016N281575_03	30-MAY-2018	Modification to informal interim and Group 2 analysis plans.

2. SUMMARY OF KEY PROTOCOL INFORMATION

2.1. Changes to the Protocol Defined Statistical Analysis Plan

Changes from the originally planned statistical analysis specified in the protocol are outlined in [Table 1](#).

Table 1 Changes to Protocol Defined Analysis Plan

Protocol	Reporting & Analysis Plan	
Statistical Analysis Plan	Statistical Analysis Plan	Rationale for Changes

 To compare the IV pharmacokinetics of oxytocin between Cohort A and Cohort B. 	
 To produce summary statistics for IV Bolus and IV infusion by Cohort 	
 Some participants, received IV Bolus dose and some participants received IV infusion dose. As the number of participants that received IV bolus and IV infusion are too small to allow for a formal stats analysis comparison, summary statistics will be presented instead.

 All Subjects Population 	
 All Subjects population label changed to Safety population. 	
 To be compliant with the new RAP template

 Enrolled Population (Defined as all subjects who were enrolled for the trial irrespective of whether they were randomized or not and for whom a record exists on the study database. This population will be used for summarizing screening failure reasons. 	
 All participants who passed screening and entered the study including randomized participants and run in failures 
Note: Screening failures (who never passed screening even if rescreened) and participants screened but never enrolled into the study (Reserve, Not Used)
	
 To be compliant with the new RAP template

CONFIDENTIAL

205920

Protocol	Reporting & Analysis Plan	
Statistical Analysis Plan	Statistical Analysis Plan	Rationale for Changes
	are excluded from the Enrolled population as they did not enter the study.	

2.2. Study Objective(s) and Endpoint(s)

Group 1 – Women in Third Stage of Labour (TSL)

Objectives	Endpoints
Primary Objectives	Primary Endpoints

 To characterize the pharmacokinetics of single doses of IH oxytocin and 10 International Units (I.U.) IM oxytocin in women in TSL. 	
 Plasma concentration time profile for IH oxytocin and 10 I.U. IM oxytocin. PK parameters: Maximum observed plasma concentration (C_{max}), Observed plasma concentrations at 10 minutes (min) postdose (C_{p10}), Observed plasma concentrations at 20 min post-dose (C_{p20}), Observed plasma concentrations at 30 min post-dose (C_{p30}), Time to C_{max} (t_{max}), Area under concentration-time curve (AUC), and Terminal phase half-life (t_{1/2}) will be calculated as data permit.
Secondary Objectives	Secondary Endpoints

 To evaluate the safety and tolerability of inhaled oxytocin. To compare pharmacokinetics of IH oxytocin to 10 I.U. IM oxytocin in women in TSL. 	
 General safety parameters: adverse events (AE); absolute values and changes over time of vital signs (blood pressure, heart rate, respiratory rate, temperature). C_{max}, C_{p10}, C_{p20}, C_{p30}, Area under the concentration-time curve from time zero (pre-dose) to three hours (h) (AUC[0-3h]) will be compared as data permit.
Exploratory Objectives	Exploratory Endpoints

 Pharmacodynamic effect of IH oxytocin and 10 I.U. IM oxytocin in women in TSL. Participant feedback regarding ease of use, instructions, and perceived ability of patients to use the ROTAHALER. 	
 Pre and post-delivery haemoglobin Questionnaire results from participants.

Group 2 – Non-pregnant, non-lactating females of child bearing potential

Objectives	Endpoints
Primary Objectives	Primary Endpoints

 To evaluate the safety and tolerability of IH and IV Oxytocin 	
 General safety parameters: adverse events; absolute values and changes over time of vital signs (blood pressure, heart rate) and 12-lead electrocardiogram (ECG) parameters (PR, QRS, QT, Corrected QT interval [QTc] intervals) from pre-dose values. Specific respiratory safety parameters: adverse respiratory events as monitored by spirometry including Forced expiratory volume at 1 minute (FEV_{1.0}), respiratory rate, and pulse oximetry.

 To characterize the pharmacokinetics 	
 Plasma concentration time profile for IH oxytocin and 5

CONFIDENTIAL

205920

Objectives	Endpoints
of single doses of IH oxytocin and 5 I.U. IV oxytocin.	I.U. IV oxytocin. 
 PK parameters: Cmax, Cp10, Cp20, Cp30, tmax, AUC, Plasma clearance (CL), volume of distribution and t1/2 will be calculated as data permit.
Exploratory Objectives	Exploratory Endpoints

 To evaluate endogenous plasma oxytocin concentrations in non-pregnant females in the presence and absence of the combined oral contraceptive. 	
 Pre-dose plasma concentrations of oxytocin.

 To compare the IH pharmacokinetics of oxytocin between Cohort A (subjects on combined oral contraceptive) and Cohort B (subjects using a non-hormonal form of contraception). 	
 Cp10, Cp20, Cp30, Cmax, AUC(0-3h), Area under the concentration time curve from time zero to infinity (AUC[0-∞]) and t1/2, will be compared as data permit.

 To compare the IV pharmacokinetics of oxytocin between Cohort A and Cohort B. 	
 Cmax, AUC, t1/2, CL and Volume of distribution (VOD) will be compared as data permit.

Groups 1 and 2 – Women in TSL and Non-pregnant, non-lactating females of child bearing potential

Objectives	Endpoints
Primary Objectives	Primary Endpoints

 To compare pharmacokinetics of IH oxytocin between Group 1 and Group 2 	
 Cp10, Cp20, Cp30, AUC(0-3h) Cmax, AUC(0-3h) AUC(0-∞), and t1/2 will be compared as data permit.

CONFIDENTIAL

205920

2.3. Study Design

Overview of Study Design and Key Features	

Group 1 – Women in TSL
 <pre> graph LR A[Screening (Pregnant Subjects)] --> B[Randomisation to treatment assignment] B --> C[Oxytocin Administration as Active Management of TSL (IM or IH) - Single dose] C --> D[Follow-up 1 (within 24 hours)] D --> E[Follow-up 2 (7-14 days)] </pre> 
Group 2 – Non-pregnant, non-lactating females of child bearing potential
 <pre> graph LR A[Screening (non-pregnant volunteers)] --> B[Randomisation to treatment assignment] B --> C[Oxytocin Administration (IH or IV) - Session 1] C --> D[Minimum 48 hours maximum 14 days] D --> E[Oxytocin Administration (IH or IV) - Session 2] E --> F[Follow-up (7-21 days)] </pre>	
Design Features	
 • Group 1: This is an open-label, randomized, single dose study enrolling women in the third stage of labour who will receive either IH or IM oxytocin • Group 2: This is an open-label, randomized, two dosing, cross over study enrolling healthy, non-pregnant, non-lactating female subjects of childbearing potential who will receive IH oxytocin at one dosing session and IV oxytocin at the other dosing session. It will be divided into two cohorts: Cohort A will enrol women on a combined oral contraceptive. Cohort B will enrol women who are not using a hormonal form of contraceptive.
Dosing	
 • Group 1: Subjects will receive 400 mcg IH oxytocin or 10 I.U. IM oxytocin in one dosing session. Follow Up 1 within approximately 24 hours post dose. Follow Up 2 at least 7 days and no greater than 14 days after study drug administration. • Total duration: Screening after 18th week of pregnancy (i.e. within 168 days of 1 dosing session) + follow up of 7 - 14 days = approximately 183 days • Group 2: Subjects will receive 400 mcg IH oxytocin and 5 I.U. IV oxytocin in two dosing sessions. Follow Up will take place at least 7 days and no greater than 21 days after last study drug administration. • Total duration: Screening within 28 days of dosing session 1 + 2 dosing sessions with a maximum of 14 days between dosing + follow-up of 7 – 21 days = 64 days
Time & Events	
 • [Refer to Appendix 2: Schedule of Activities]
Treatment Assignment	
 • Group 1: Subjects will be randomised to receive one of the following study treatments: A: 400 mcg IH oxytocin B: 10 I.U. IM oxytocin • Group 2: Subjects will receive both of the following study treatments over the course

CONFIDENTIAL

205920

Overview of Study Design and Key Features	
	of two dosing sessions: C: 400 mcg IH oxytocin D: 5 I.U. IV oxytocin
Interim Analysis	
 No formal Interim Analysis are planned, however, PK samples will be analysed and preliminary PK parameters derived following completion of approximately 5 women on each treatment group: 400 mcg IH and 10 I.U. IM to women in TSL (Group 1) and 400 mcg IH to non-pregnant women on the combined oral contraceptive (Group 2 Cohort A), in order to assess if dose escalation is required.

2.4. Statistical Hypotheses / Statistical Analyses

No formal hypotheses will be tested, however, the following comparison is of interest:

- Cohort A (inhaled oxytocin) vs Cohort B (inhaled oxytocin)

For each PK endpoint of interest, point estimates and corresponding two-sided 90% confidence intervals will be constructed for the ratio of the geometric mean of the test treatment to the geometric mean of the reference treatment, $\mu(\text{test})/\mu(\text{reference})$ to provide the range of plausible values for the comparisons of interest.

For IV oxytocin, summary statistics will be produced separately for IV Bolus Oxytocin and IV Infusion Oxytocin. Due to small participant numbers, a formal statistical analysis to compare Cohort A vs Cohort B is not possible for IV Bolus or for IV infusion.

CONFIDENTIAL

205920

3. PLANNED ANALYSES: GROUP 2

3.1. Interim Analyses: Group 2

No formal Interim Analysis are planned, however, PK samples will be analysed and preliminary PK parameters derived following completion of approximately 5 women on each treatment group: 400 mcg IH and 10 I.U. IM to women in TSL (Group 1) and 400 mcg IH to non-pregnant women on the combined oral contraceptive (Group 2 Cohort A), in order to assess if dose escalation is required.

3.2. Final Analyses

An analysis of Group 2 (non-pregnant volunteers) will be performed once Group 2 has completed to allow for full reporting of non-pregnant volunteer data prior to completion of Group 1.

The final planned primary analyses for Group 2 will be performed after the completion of the following sequential steps:

1. All participants in group 2 have completed the study as defined in the protocol
2. All required database cleaning activities have been completed for group 2 and final database release (DBR) and database freeze (DBF) for group 2 has been declared by Data Management.
3. All criteria for unblinding the randomization codes for group 2 have been met.
4. Randomization codes for group 2 have been distributed according to RandAll NG procedures.

4. ANALYSIS POPULATIONS

Population	Definition / Criteria	Analyses Evaluated
Screened	
 All participants who were screened for eligibility 	
 Screen Failures
Enrolled	
 All participants who passed screening and entered the study including randomized participants and run in failures 
Note: Screening failures (who never passed screening even if rescreened) and participants screened but never enrolled into the study (Reserve, Not Used) are excluded from the Enrolled population as they did not enter the study.
	
 Study Population
Safety	
 Comprise of subjects who receive at least one dose of study medication. This population will be used for the study population and safety displays. 
Note: This population will be based on the treatment the participants actually received
	
 Study Population Safety
Pharmacokinetic (PK)	
 Subjects in the 'Safety' population for whom a pharmacokinetic sample was obtained and analysed. PK population will be the population for reporting PK data. 	
 PK

Refer to [Appendix 12](#): List of Data Displays which details the population used for each display.

CONFIDENTIAL

205920

4.1. Protocol Deviations

Protocol deviations will be tracked by the study team throughout the conduct of the study in accordance with the Protocol Deviation Management Plan.

- Data will be reviewed prior to freezing the database to ensure all important deviations are captured and categorised on the protocol deviations dataset.
- The SI dataset will include all protocol deviations; the analysis dataset will include only important protocol deviations. The analysis dataset will be used for the listing of important protocol deviations.
- The study endpoints will be reported using the populations detailed in Section 4 of this document regardless of whether the participants deviate from the protocol.
- A separate listing of all inclusion/exclusion criteria deviations will also be provided. This listing will be based on data as recorded on the inclusion/exclusion page of the eCRF.

CONFIDENTIAL

205920

5. CONSIDERATIONS FOR DATA ANALYSES AND DATA HANDLING CONVENTIONS

5.1. Study Treatment & Sub-group Display Descriptors: Group 2

Treatment Group Descriptions			
RandAll NG		Data Displays for Reporting	
Code	Description	Description	Order in TLF
C	400 mcg IH oxytocin	400 mcg IH	1
D1	5 I.U. IV oxytocin	8.5 mcg IV bolus	2
D2	5 I.U. IV oxytocin	8.5 mcg IV Infusion	3

Treatment comparisons will be displayed as follows using the descriptors as specified:

1. IH Oxytocin (COC) vs IH Oxytocin (non-COC)

If the duration of IV oxytocin dose administered is less than or equal to 2min then the IV dose administered is an IV Bolus dose. If the duration of IV oxytocin dose administered is greater than 2 min then the IV dose administered is an IV Infusion dose. The tables/listings that would display the statistics should display IV oxytocin administered as IV Bolus Oxytocin and IV Infusion Oxytocin. Subjects assigned to treatment code D and received the IV via bolus will be labelled as D1 and those who received IV via infusion will be labelled as D2.

The treatment dosage will be included in the footnotes for the respective tables/listings. If treatment codes have been displayed in the tables/listings the treatment descriptions should be included as footnotes. COC refers to Combined Oral Contraceptive and non-COC refers to non-Combined Oral Contraceptive.

5.2. Baseline Definitions

For all endpoints (except as noted in baseline definitions) the baseline value will be the latest pre-dose assessment with a non-missing value. If time is not collected, Day 1 assessments are assumed to be taken prior to first dose and used as baseline.

CONFIDENTIAL

205920

Baseline definitions for Group 2

Parameter	Study Assessments Considered as Baseline			Baseline Used in Data Display
	Screening	Day -1	Day 1 (Pre-Dose)	
Safety				
Vital Signs (pressure, heart rate, temperature, respiratory rate)	X	X	X	Day 1
LAB	X	X	X	Day 1
ECG	X	X	X	Day 1
FEV1	X	X	X	Day 1

Unless otherwise stated, if baseline data is missing no derivation will be performed and baseline will be set to missing.

5.3. Other Considerations for Data Analyses and Data Handling Conventions

Other considerations for data analyses and data handling conventions are outlined in the appendices:

Section	Component
10.3	Appendix 3: Assessment Windows
10.4	Appendix 4: Study Phases and Treatment Emergent Adverse Events
10.5	Appendix 5: Data Display Standards & Handling Conventions
10.6	Appendix 6: Derived and Transformed Data
10.7	Appendix 7: Reporting Standards for Missing Data
10.8	Appendix 8: Values of Potential Clinical Importance

CONFIDENTIAL

205920

6. STUDY POPULATION ANALYSES : GROUP 2

6.1. Overview of Planned Study Population Analyses

The study population analyses will be based on the Safety & Enrolled population, with screen failures as an exception. The study population displays will be produced page wise, grouped by cohorts A and B

Study population analyses including analyses of subject's disposition, protocol deviations, demographic and baseline characteristics, prior and concomitant medications, and exposure and treatment compliance will be based on GSK Core Data Standards.

Details of the planned displays are provided in [Appendix 12: List of Data Displays](#) and will be based on GSK data standards and statistical principles.

CONFIDENTIAL

205920

7. SAFETY ANALYSES : GROUP 2

The safety analyses will be based on the Safety population, unless otherwise specified.

7.1. Adverse Events Analyses

Adverse events analyses including the analysis of adverse events (AEs), Serious (SAEs) and other significant AEs will be based on GSK Core Data Standards. The details of the planned displays are provided in [Appendix 12: List of Data Displays](#).

7.2. Clinical Laboratory Analyses

Laboratory evaluations including the analyses of Chemistry laboratory tests, Hematology laboratory tests, Urinalysis, and liver function tests will be based on GSK Core Data Standards. The details of the planned displays are in [Appendix 12: List of Data Displays](#).

7.3. Other Safety Analyses

The analyses of non-laboratory safety test results including ECGs and vital signs will be based on GSK Core Data Standards, unless otherwise specified. The details of the planned displays are presented in [Appendix 12: List of Data Displays](#).

CONFIDENTIAL

205920

8. PHARMACOKINETIC ANALYSES : GROUP 2

8.1. Primary Pharmacokinetic Analyses : Group 2

8.1.1. Endpoint / Variables : Group 2

- Plasma concentration time profile for IH oxytocin and 5 I.U. IV oxytocin.
- PK parameters: C_{max}, C_{p10}, C_{p20}, C_{p30}, t_{max}, AUC(including AUC(0-t), AUC(0-inf) and AUC(0-3h)), Plasma clearance (CL), volume of distribution and t_{1/2} will be calculated as data permit

8.1.1.1. Drug Concentration Measures : Group 2

Refer to [Appendix 5: Data Display Standards & Handling Conventions \(Section 10.5.3. Reporting Standards for Pharmacokinetic\)](#)

8.1.1.2. Derived Pharmacokinetic Parameters: Group 2

Pharmacokinetic parameters will be calculated by standard non-compartmental analysis according to current working practices and GSK procedures using the currently supported version of WinNonlin. All calculations of non-compartmental parameters will be based on actual sampling times. Pharmacokinetic parameters listed will be determined from the plasma concentration-time data, as data permits.

Treatment	Parameter	Parameter Description
IH/IV	C _{max}	Maximum observed concentration, determined directly from the concentration-time data.
IH/IV	Pre - dose	Quantified concentration in PK sample collected at predose, determined directly from the concentration-time data.
IH	C _{p10}	Quantified concentration in PK sample collected at 10 minutes (nominal time) post-dose, determined directly from the concentration-time data.
IH	C _{p20}	Quantified concentration in PK sample collected at 20 minutes (nominal time) post-dose, determined directly from the concentration-time data.
IH	C _{p30}	Quantified concentration in PK sample collected at 30 minutes (nominal time) post-dose, determined directly from the concentration-time data.
IH/IV	t _{max}	Time to reach C _{max} , determined directly from the concentration-time data.
IH/IV	AUC(0-t)	Area under the concentration-time curve from time zero to the time of the last quantifiable concentration (C(t)) will be calculated using the linear trapezoidal rule for each incremental trapezoid and the log trapezoidal rule for each decremental trapezoid.
IH/IV	AUC (0-inf)	Area under the concentration-time curve extrapolated to infinity will be calculated as: $AUC = AUC(0-t) + C(t) / \lambda_{z}$
IH/IV	AUC(0-3h)	Area under the concentration-time curve from time zero to 3 h post-dose
IV	Plasma clearance (CL)	Plasma clearance (a volume per time, i.e. a flow) expresses the overall ability of the body to eliminate a drug by scaling the drug elimination rate (amount per time) by the corresponding plasma concentration level.

CONFIDENTIAL

205920

Treatment	Parameter	Parameter Description
IV	VOD	Volume of distribution of a drug gives information on its distribution in the body. Calculated as $VD = \text{Total amount of drug in the body} / \text{Drug blood plasma concentration}$.
IH/IV	t1/2	Apparent terminal half-life will be calculated as: $t_{1/2} = \ln 2 / \text{Lambda}_z$ (NOTE: Lambda_z is the terminal phase rate constant).
IH/IV	Clast	Last observed quantifiable concentration
IH/IV	tlast	Time of the last observed quantifiable concentration
IH/IV	Lambda_z	The first order rate constant associated with the terminal (log-linear) portion of the concentration-time curve.
IH/IV	Lambda_z_lower	First time point used in computing Lambda_z .
IH/IV	Lambda_z_upper	Last time point used in computing Lambda_z .
IH/IV	#pts	Number of points used in computing Lambda_z .
IH/IV	r-squared	R-squared of Lambda_z computation.
IH/IV	AUC(0-inf)/D	AUC(0-inf) corrected for dose

NOTES:

- Additional parameters may be included as required.

The absolute bioavailability (F) will be derived for each subject using the formula outlined below. If dose normalised AUC(0-∞) cannot be determined this will be substituted with dose normalised AUC(0-t) for that profile. All PK parameters (including the derived inhaled bioavailability, F) will be listed and summarised.

$$F = \frac{AUC(0-\infty)_{inhalad} / Dose_{inhalad}}{AUC(0-\infty)_{IV} / Dose_{IV}}$$

The conversion factor to normalise IV doses is 1 IU = 1.7 mcg oxytocin

8.1.2. Summary Measure: Group 2

Pharmacokinetic data will be presented in graphical and/or tabular form and will be summarized descriptively by IH oxytocin , IV Bolus Oxytocin, IV Infusion Oxytocin for each Cohort (Cohort A and Cohort B). In addition data for the derived absolute bioavailability, F will also be summarised by cohort.

For each of the parameters the following summary statistics will be calculated

- **Untransformed Data:** N, n, arithmetic mean, 90% confidence interval (CI) for the arithmetic mean, standard deviation (SD), median, minimum, maximum.
- **Loge-transformed Data:** Geometric mean, 90% CI for the geometric mean, standard deviation (SD) of loge-transformed data and %CVb.

For tmax, and t½ the summary statistics specified for untransformed data above will be

CONFIDENTIAL

205920

generated.

8.1.3. Population of Interest : Group 2

The primary pharmacokinetic analyses will be based on the Pharmacokinetic population, unless otherwise specified.

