2.4. Statistical Hypotheses / Statistical Analyses

No formal hypotheses will be tested.

For IH and IM oxytocin, summary statistics will be produced separately for IH Oxytocin and IM Oxytocin. Due to sparse PK concentrations, it is not possible to include a formal statistical analysis to compare IH and IM Oxytocin. PK parameters will be derived as data permit. Individual plots, listings and summary tables will be produced for available PK concentration data. Only listings and summary tables will be produced for PK Parameter data.

3. PLANNED ANALYSES: GROUP 1

3.1. Interim Analyses: Group 1

No formal Interim Analysis are planned, however, PK samples will be analysed and preliminary PK parameters derived following completion of approximately 5 women on each treatment group: 400 mcg IH and 10 I.U. IM to women in TSL (Group 1) and 400 mcg IH to non-pregnant women on the combined oral contraceptive (Group 2 Cohort A), in order to assess if dose escalation is required.

Due to sparse PK concentration-time data available following administration of IH and IM oxytocin to women in TSL, only concentration time plots were presented at the interim analysis. The Study has been terminated early due the unanticipated inability to be able to quantify plasma oxytocin using a selective and sensitive (LLQ 2pg/mL) analytical assay due to low oxytocin concentrations (<2pg/mL) in the majority of samples collected from women in Third Stage Labour (TSL), following either IM or IH administration. Therefore, the Primary objective of the study to characterise the PK of single doses of IH and IM oxytocin in women in TSL, cannot be met, and the study is being terminated

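### Group 2 RAP 8.1.1.2: absolute bioavailability F can divide a truncated AUC by an extrapolated one within the same woman, and such mixed ratios are pooled with matched ones in the F summaries

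*SAP*

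**What the plan says.** Group 2 is a crossover in healthy women "who will receive IH oxytocin at one dosing session and IV oxytocin at the other dosing session" (section 2.3), so a woman who completes both sessions has one inhaled and one IV profile.

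Section 8.1.1.2 of the Group 2 RAP states: "The absolute bioavailability (F) will be derived for each subject using the formula outlined below". The formula is dose-normalised AUC(0-∞) inhaled over dose-normalised AUC(0-∞) IV. The fallback is: "If dose normalised AUC(0-∞) cannot be determined this will be substituted with dose normalised AUC(0-t) for that profile".

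The parameter table in the same section defines AUC(0-∞) as AUC(0-t) + C(t)/lambda_z, and AUC(0-t) as the area up to that profile's own last quantifiable concentration.

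On reporting, section 8.1.2 adds: "In addition data for the derived absolute bioavailability, F will also be summarised by cohort". The statistics listed there include arithmetic and geometric means, each with a 90% CI. Section 10.5.2 lists F beside AUC(0-t), AUC(0-∞), tlast and the lambda_z diagnostics. No flag for substituted values is planned, and no summary without them.

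**The concern.** The fallback works one profile at a time. If one of a woman's two profiles has no AUC(0-∞), only that side of her ratio changes. One area then stops at the last quantifiable concentration while the other runs to infinity, and the missing tail does not cancel. Her F is too low if the inhaled profile was the one replaced, and too high if the IV profile was.

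F is the plan's within-woman ratio of inhaled to IV exposure. If some values in a cohort are matched ratios and others mixed, the cohort mean and its interval describe no single quantity. The reader of the summary table cannot tell how much of the result comes from substitution.

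**Working it through.** **Inputs from the Group 2 RAP.** The formula for F, the fallback, and the definitions of AUC(0-t) and AUC(0-∞), all in 8.1.1.2. The IV dose conversion is in the same section: "The conversion factor to normalise IV doses is 1 IU = 1.7 mcg oxytocin".

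**Input not in the documents.** e = [AUC(0-∞) − AUC(0-t)] / AUC(0-∞), the share of the area after tlast. It is assumed below over a range.

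**Check of the plan's own figure.** The RAP gives no numerical value for F. The one figure that feeds it is the IV dose: 5 I.U. × 1.7 = 8.5 mcg, which agrees with the display descriptors in section 5.1. Dose normalisation is not the problem.

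**Step 1: one woman.** From the definitions, AUC(0-t) = (1 − e) × AUC(0-∞). Hence

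- inhaled profile only substituted: F reported / F = 1 − e_IH
- IV profile only substituted: F reported / F = 1 / (1 − e_IV)
- both substituted: F reported / F = (1 − e_IH) / (1 − e_IV)

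| e (assumed) | inhaled only | IV only |
|---|---|---|
| 5% | ×0.95 | ×1.05 |
| 10% | ×0.90 | ×1.11 |
| 20% | ×0.80 | ×1.25 |
| 30% | ×0.70 | ×1.43 |
| 40% | ×0.60 | ×1.67 |

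If both are substituted, the errors cancel only when the two shares are equal: 20% and 20% gives ×1.00, inhaled 40% with IV 10% gives 0.60/0.90 = ×0.67, and inhaled 10% with IV 40% gives 0.90/0.60 = ×1.50.

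**Step 2: a cohort.** If a fraction p of women have one side substituted at a common e, the geometric mean of F is multiplied by (1 − e)^p for inhaled substitution, or (1 − e)^(−p) for IV. With p = 0.5 (assumed) and e from 10% to 40%, that is ×0.95 to ×0.78 (inhaled) or ×1.05 to ×1.29 (IV).

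**Step 3: is that range of e conceivable?** For a mono-exponential decline followed down to the assay limit, e is about LLQ/Cmax. The only limit stated is in section 3.1 of the Group 1 RAP, "using a selective and sensitive (LLQ 2pg/mL) analytical assay". If it also applies to Group 2 (an assumption), e is 2/5 = 40%, 2/10 = 20%, 2/20 = 10% and 2/100 = 2% at assumed peaks of 5, 10, 20 and 100 pg/mL. The range is possible at low peaks and negligible at high ones. The documents do not say which holds in Group 2.

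**Step 4: can it be corrected afterwards?** No. Where AUC(0-∞) cannot be determined, e for that profile cannot be determined either.

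**The case against.** The strongest reply concerns importance. F is absent from the Group 2 objectives and endpoints (section 2.2), from the comparison of interest (2.4) and from the Cohort A versus Cohort B models (8.3.4). It is only listed and summarised. The listing in 10.5.2 also lets a careful reader spot a substituted profile, because its AUC(0-∞) will be missing. Both points stand and limit the weight of the issue. Neither repairs the summary statistic. Section 10.5.3 also refers to an outside standard for parameters affected by non-quantifiable values. Its content is not shown, so it cannot be counted as a remedy for the explicit rule in 8.1.1.2.

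Two stronger readings are tempting. First, a reader might infer that the bias runs systematically one way by route, because low inhaled profiles lose their terminal phase more readily. The documents give no Group 2 concentrations or failure rates. The widespread non-quantifiable samples are reported for women in third stage labour, and section 2.1 of the Group 1 RAP calls those inhaled data sparse relative to Group 2, which has 15 post-dose samples to 4 h.

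Second, a reader might infer a spurious contraceptive effect on F. With e = 30% and inhaled substitution in 20% of one cohort and 60% of the other, a true cohort ratio of 1 would appear as 0.7^0.2 / 0.7^0.6 = 1.15. With equal shares it stays at 1.00. Nothing in the documents favours the imbalance, and the plan makes no formal cohort contrast on F.

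**Conclusion.** The rule as written permits mixed ratios, and their direction follows from the plan's own definitions. The size per affected woman is ×(1 − e) or ×1/(1 − e): ×0.90 to ×0.60 for inhaled substitution at e of 10% to 40%, and ×1.11 to ×1.25 for IV substitution at e of 10% to 20%. The values of e are assumed, and the number of affected women is unknown. The consequence is confined to the descriptive summaries of F. Neither a systematic bias by route nor a false cohort difference is shown. The point is modest, but the wording can be corrected at little cost.

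**What to change.** Amend 8.1.1.2 and 8.1.2 of the Group 2 RAP as follows:

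- Base the main summary of F on women with AUC(0-∞) determined in both profiles.
- Flag in the listing every F that uses a substituted AUC, and show which profile was substituted.
- Present the summary that includes substituted values as supportive only, with the number substituted by route and cohort.

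Two apparent alternatives should not become the rule. AUC(0-t) on both sides removes the mixture but is unbiased only when the two shares are similar (see ×0.67 and ×1.50 above). Cutting both profiles at the smaller tlast can bias F low when inhaled absorption is still continuing. To illustrate, take a one-compartment model with elimination rate k and first-order inhaled absorption rate ka (rates assumed), where only the IV profile lacks AUC(0-∞), its tlast sets the cut, and x = e is the IV share beyond it. At ka = 2k the cut gives (1 − x)²/(1 − x) = 1 − x, so ×0.90 at 10%. At ka = k it gives [1 − x(1 − ln x)]/(1 − x) = 0.670/0.90 = ×0.74 at 10%, against ×1.11 under the present rule. With fast absorption (ka = 5k) it does better, ×0.97, but the kinetics are not known in advance.

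The cost is a wording change, a filter and a listing flag, with no new data. The downside is fewer women in the main F summary, possibly selected for well-defined terminal phases. That is why the summary with substituted values is kept as supportive.
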